7.4. Medical and Surgical Procedures

Medical and surgical procedures will be classified and presented as follows:

- Prior medical and surgical procedures: CCI [REDACTED]
- Concomitant medical and surgical procedures: CCI [REDACTED]

If the start date and/or stop date and 'ongoing' are missing then the medical and surgical procedure will be considered CCI [REDACTED].

Medical and surgical procedures be coded using MedDRA, Version 21.1.

CCI [REDACTED]

Medical and surgical procedures (prior and concomitant) will be summarized using the number and percent of subjects reporting each SOC and PT and sorted by descending overall total of SOC and PT. Summary tables will be presented for ITT population.

Medical and surgical procedures listings will be sorted by subject number, onset date, end date, SOC, and PT.

7.5. Medications

CCI

All medications will be listed.

CCI

CCI

8. Efficacy

All efficacy assessments will be summarized by visit using descriptive statistics. A two-sided 95% Clopper-Pearson confidence interval (CI) for success rate and a two-sided 95% Student's t-distribution CI for mean values will be included in the efficacy summary tables, if applicable.

Efficacy analyses will be performed with the observed cases (OC) and with last observation carried forward (LOCF) for data imputation for Investigator's Global Assessment (IGA), Physician's Global Assessment (PGA) and acne lesions counts on the face and trunk. Non-responder analysis will also be carried out for binary endpoints by with missing as failure (MAF) for data imputation.

8.1. Efficacy Endpoints and Analysis

8.1.1. CCI [REDACTED]

The Investigator's Global Assessment (IGA) is an instrument to evaluate the facial acne severity CCI [REDACTED]. IGA will be recorded in the CRF CCI [REDACTED] using a 5-point scale, as described in Table 3.

Table 3: Scale for acne assessment

0	Clear	Clear skin with no inflammatory or non-inflammatory lesions.
1	Almost Clear	A few scattered comedones and a few small papules.
2	Mild	Easily recognizable; less than half the surface is involved. Some comedones and some papules and pustules.
3	Moderate	More than half of the surface is involved. Many comedones, papules and pustules. One nodule may be present.
4	Severe	Entire surface is involved. Covered with comedones, numerous papules and pustules. Few nodules may be present.

IGA will be summarized by visit CCI [REDACTED] as categorical variables. All IGA data will be listed.

IGA treatment success is defined as 0 (clear) or 1 (almost clear) and at least a 2-grade improvement from baseline. The IGA treatment success rate will be summarized by visit CCI [REDACTED].

Analyses will be performed with LOCF and MAF for data imputation and with the observed cases (OC).

For the LOCF analysis, the imputation will be performed based on the recorded IGA per visit, and the imputed IGA treatment success rate will be based on the imputed values. For the MAF analysis, non-evaluable subjects will be considered as IGA treatment failures. For both LOCF and MAF analyses, the IGA treatment success rate will be calculated as the ratio between the number of subjects achieving IGA treatment success CCI [REDACTED] and the number of subjects included in the ITT population.

For the OC analysis, the IGA treatment success rate will be calculated as the ratio between the number of subjects achieving IGA treatment success CCI [REDACTED] and the number of subjects evaluable at each visit (i.e. the ones with data available at that visit).

IGA treatment success rate (LOCF) will be presented using line plots over time.

8.1.2. Physician's Global Assessment of truncal acne

The Physician's Global Assessment (PGA) is an instrument to evaluate the truncal acne severity CCI

PGA will be recorded in the CRF and assessed CCI using the 5-point scale as described in Table 3.

PGA will be summarized by visit CCI as categorical variables. All PGA data will be listed.

PGA treatment success is defined as 0 (clear) or 1 (almost clear) and at least a 2-grade improvement from baseline. The PGA treatment success rate will be summarized by visit CCI

Analyses will be performed with LOCF and MAF for data imputation and with the observed cases (OC).

For the LOCF analysis, the imputation will be performed based on the recorded PGA per visit, and the imputed PGA treatment success rate will be based on the imputed values. For the MAF analysis, non-evaluable subjects will be considered as PGA treatment failures. For both LOCF and MAF analyses, the PGA treatment success rate will be calculated as the ratio between the number of subjects achieving PGA treatment success CCI and the number of subjects included in the ITTT population.

For the OC analysis, the PGA treatment success rate will be calculated as the ratio between the number of subjects achieving PGA treatment success CCI and the number of subjects evaluable at each visit (i.e. the ones with data available at that visit).

PGA treatment success rate (LOCF) will be presented using line plots over time.

8.1.3. Acne lesions counts on the face and trunk

CCI

8.2. Subject Reported Efficacy Assessments

8.2.1. Dermatology Life Quality Index (DLQI):

DLQI is a validated 10-item questionnaire for subjects aged > 16 years, covering domains including symptoms/feelings, daily activities, leisure, work/school, personal relationships and treatment. DLQI data will be recorded in the CRF.

The total DLQI score is calculated by summing the scores of each question, resulting in a maximum of 30 and a minimum of 0. A lower score on the DLQI indicates increased QOL; therefore, negative changes

CCI

CCI

from Baseline indicate improvement. The DLQI total scores (which measure the impact of skin disease on the quality of life of an affected person) can be interpreted as: no effect (0-1), small effect (2-5), moderate effect (6-10), very large effect (11-20), or extremely large effect (21-30).

DLQI will be summarized by visit (Baseline, Week 12 and Week 24/ET) and as continuous variables. Absolute change from baseline will also be included in the descriptive analysis. All DLQI data will be listed.

8.2.2. Children's Dermatology Life Quality Index (cDLQI):

cDLQI is a comparable validated 10-item questionnaire designed for pediatric subjects aged 16 years or less. cDLQI will be reported at Baseline, Week 12 and Week 24/ET.

The total cDLQI score is calculated by summing the scores of each question, resulting in a maximum of 30 and a minimum of 0. A lower score on the cDLQI indicates increased QOL; therefore, negative changes from Baseline indicate improvement. The cDLQI total scores (which measure the impact of skin disease on the quality of life of an affected person) can be interpreted as: no effect (0-1), small effect (2-6), moderate effect (7-12), very large effect (13-18), or extremely large effect (19-30).

cDLQI will be summarized by visit (Baseline, Week 12 and Week 24/ET) as continuous variables. Absolute change from baseline will also be included in the descriptive analysis. All cDLQI data will be listed.

8.2.3. CompAQ for Facial and Truncal Acne

Subjects (16 years of age and older) are provided with the comprehensive QoL measure inclusive of facial and truncal form and instructed to read and answer all 20 quality of life questions. The questionnaire measures the impact of facial and torso acne on health-related quality of life.

The 20 questions consist of 5 domains that assess a variety of psychosocial and physical impacts of acne: Psychological/Emotional, Social (Judgement from Others), Social Interactions, Treatment Concerns, Physical Symptoms. The higher the score, the more quality of life is impaired. Each question is assessed with a numeric score between 0 (Never) and 8 (All the time).

Higher scores indicate greater adverse impact.

- The response range for each question is from 0–8 with higher numbers indicating greater adverse impact.
- For each domain, response range is from 0–32.
- For the long form questionnaire, response range is from 0–160
- For the short form questionnaire, response range is from 0–40

A final question will also assess the change in overall QoL since baseline with a numeric score between -7 (a great deal worse) and 7 (a great deal better), with 0 denoting no change in QoL.

CompAQ for Facial and Truncal Acne will be summarized by visit (Baseline, Week 12 and Week 24/ET) as continuous variables. Absolute change from baseline will also be included in the descriptive analysis. All CompAQ for Facial and Truncal Acne data will be listed.

8.2.4. EuroQoL 5-Dimension (EQ-5D-5L)

At Baseline, Week 12 and Week 24/ET, subject will complete the EQ-5D-5L questionnaire for the assessment of the general health state, which contains two parts: a descriptive system and a VAS.

The descriptive system is made up of five dimensions: mobility, self-care, usual activities, pain/discomfort and anxiety/depression. The VAS consists of a vertical line where the subject can assess his or her own

CCI

CCI

health status with a numerical value between 100 (Best imaginable health state) and 0 (Worst imaginable health state).

Each of the 5 dimensions comprising the EQ-5D descriptive system is divided into 5 levels of perceived problems:

- Level 1: indicating no problem.
- Level 2: indicating slight problems.
- Level 3: indicating moderate problems.
- Level 4: indicating severe problems.
- Level 5: indicating extreme problems.

A unique Health State is defined by combining 1 level from each of the 5 dimensions.

A total of 3125 possible Health States is defined in this way. Each state is referred to in terms of a 5 digit code. For example, state 11111 indicates no problems on any of the 5 dimensions, while state 12345 indicates no problems with mobility, slight problems with washing or dressing, moderate problems with doing usual activities, severe pain or discomfort and extreme anxiety or depression.

EQ-5D-5L Health States, defined by the EQ-5D-5L descriptive system, have to be converted into EQ-5D-5L Index Scores using country specific value sets.

For the US, the EQ-5D-5L Index Score ranges from -0.109 (corresponding to the Health State 55555) to 1.000 (corresponding to the Health State 11111).

EQ-5D-5L Index Score and VAS will be summarized by visit (Baseline, Week 12 and Week 24/ET) as continuous variables. Absolute change from baseline will also be included in the descriptive analysis.

EuroQoL 5-Dimension health profiles (i.e. the levels for mobility, self-care, usual activities, pain/discomfort and anxiety/depression) will be summarized by visit (Baseline, Week 12 and Week 24/ET) using frequency tables.

EuroQoL 5-Dimension levels, index score and VAS will be listed.

CCI

CCI

CCI

CCI

CCI

CCI

CCI

9. Analysis Of Pharmacokinetics

Not applicable in this study.

CCI

CCI

10. Analysis Of Pharmacodynamics

Not applicable in this study.

CCI

CCI

11. Safety

The population used for safety analyses will be the SAF. All data for all safety assessments will be presented in data listings.

11.1. Extent of Exposure and Study Duration

The extent of exposure and the number of subjects exposed to study drug will be summarized.

CCI

11.2. Missing Applications and Dose Reductions

The occurrence of missed applications since last scheduled visit, the occurrence of prescribed dose reductions and the reasons for dose reduction since last scheduled visit will be summarized separately for Face and Trunk by visit CCI using the summary statistics for categorical variables.

The number of missed application since last scheduled visit and the number of missed application since last scheduled visit due to dose reductions will be summarized separately for Face and Trunk by visit CCI using summary statistics for continuous variables.

11.3. Treatment Compliance

Treatment compliance will be calculated as the ratio (expressed as percentage) between the number of actual applications and the number of expected applications.

CCI

11.4. Adverse Events

Adverse events (AEs) will be coded using MedDRA Version 21.1. Summaries of AEs will include only treatment-emergent AEs (TEAEs) defined as AEs with an onset date on or after the date of first treatment. AEs with missing onset dates will be considered as TEAEs.

TEAEs will be summarized using the number and percent of subjects reporting each SOC and PT and sorted by descending overall total of SOC and PT. Subjects who experienced multiple events within the

CCI

CCI

same SOC will be counted once in the SOC summary. Subjects who experienced multiple occurrences of events with the same PT will be counted once in the PT summary. Percentages will be calculated using the total number of subjects in the SAF.

If a subject experiences more than 1 occurrence of the same AE, the occurrence with the greatest severity and the closest association with the study drug will be used in summary tables. TEAEs related to study drug are those for which a 'Reasonable Possibility' of relationship is reported in the CRF, or with missing relationship.

CCI

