Analysed variables	
Subject-reported outcomes
 
 DLQI/cDLQI and CompAQ at Baseline and Week 12, 24/Early termination Subject satisfaction questionnaires at Week 12, 24/Early termination EQ-5D-5L at baseline and Week 12, 24/Early termination 
Efficacy variable
 
 CCI [REDACTED] Percent change in the facial IL NI CCI [REDACTED] lesion count from Baseline to Weeks 12 and 24 CCI [REDACTED] Percent change in the trunk IL, NI CCI [REDACTED] lesion count from Baseline to Weeks 12 and 24 Success rate of IGA as the percentage of subjects who achieved an IGA with a score of 1 (almost clear) or 0 (Clear) AND an at least a 2-grade improvement from Baseline at each study visit. Success rate of PGA as the percentage of subjects who achieved a PGA with a score of 1 (almost clear) or 0 (Clear) AND an at least a 2-grade improvement from Baseline at each study visit. 
CCI [REDACTED]
 
CCI [REDACTED]
 
Safety variables
 
 Local tolerability parameters will be assessed at Baseline and each post baseline visits, on all treated areas. CCI [REDACTED] Local tolerance: Raw value at each visit and worst-score across visit, % of Subjects across scores at each post-baseline visit Incidence of adverse events (AESI, SAEs, Death, leading to discontinuation or early termination) 
Other
 
CCI [REDACTED]

Principal statistical method:	
The Intent-to-Treat (ITT) population consists of all enrolled subjects. The Safety population (SAF) consists of the ITT population, who applied at least one dose of treatment.
 
The main objective of this study is to evaluate the subject reported outcomes with trifarotene with 12 and up to 24 weeks of treatment.
 
All variables will be descriptively summarized. All safety endpoints will be summarized based on SAF population and Quality of life and Efficacy endpoints will be summarized

SYNOPSIS	
Clinical Trial Title: A Multi-Center Study to Evaluate Subject Reported Outcomes with use of Trifarotene 50 µg/g Cream in the Treatment of Moderate Facial and Truncal Acne Vulgaris	

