4 CLINICAL TRIAL DURATION AND TERMINATION

The planned clinical trial duration (from FSI to LSO) is approximately CCI. The date of end of the clinical trial is defined as the date of the last visit of the last subject who participates in the trial.

The planned duration of recruitment (i.e. From FSI to LSI) is approximately CCI.

Prior to subject enrolment, a screening period lasting CCI at the maximum is authorized.

Clinical trial participation for each subject is approximately CCI

GALDERMA may decide to prematurely terminate or suspend the participation of a particular clinical trial center (e.g., for non-inclusion or non-compliance with protocol, regulations, or GCP) or prematurely suspend the clinical trial (e.g., for safety, study drug quality, regulatory, efficacy, or logistical reasons) at any time, with appropriate notification.

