6.1.4 Instructions for use and application

Each subject will receive both oral and written instructions for the proper dosing and study treatment application techniques. CCI

CCI

As well, the dosing calendar completion will be explained to each subject at each dispensation visit.

Applications will be done by the subjects themselves at home in the evening. CCI

CCI

Application on the face:

CCI

CCI

The study drug will be applied to the facial region which includes the forehead, nose, chin and each cheek once daily in the evening after washing and drying.

The objective is to cover the face with a thin layer of the study drug, CCI One pump actuation should be enough to cover the forehead, right cheek, left cheek, nose, and chin. Avoid application in/close to eyes, or angles of the mouth, lips and mucous membrane.

CCI

Application on the trunk:

CCI

The study drug will be applied to the upper truncal regions CCI once daily in the evening after washing and drying.

The objective is to cover the reachable upper truncal region with a thin layer of the study drug, CCI Two actuations of the pump should be enough to cover right and left upper back area CCI and upper anterior right and left chest. Avoid application on the axillary region and anterior and posterior neck.

The study drug should not be applied to cuts, abrasions, eczematous, or sunburned skin.

The daily diary is to be completed by the subject (if needed, with the help of the legal guardian) and returned to the site at each study visit.

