9.1.3 Data presentation and graphics

For statistical analyses purpose, baseline is defined as the last measurement prior to the first application of the study drug and all analyses will be summarized by visits.

For the summary statistics, the categorical data will be summarized by frequency and percentage of subjects for each response category (N, %) and the continuous data will be summarized using number of subjects, mean, median, minimum, maximum, and standard deviation.

Subject disposition, demographics and baseline characteristics, previous therapies, and concomitant therapies will be summarized by descriptive statistics based on the ITT Population. Treatment exposure and compliance data will be summarized based on the Safety Population.

For statistical analysis purposes, previous therapies/procedures are defined as those ending at Baseline or before; and concomitant therapies/procedures are defined as those ongoing at the Baseline visit or starting after the Baseline visit.

Treatment-emergent Adverse Events (TEAEs) are defined as AEs with onset on or after first dose of study drug; or those AEs with onset prior to first dose of study drug but worsened during treatment.

TEAEs will be tabulated in frequency tables by System Organ Class (SOC) and Preferred Term (PT) based on the Medical Dictionary for Regulatory Activities (MedDRA). Additional summary tables will be provided for SAEs, AEs considered related to the study drug, severe AEs, AESIs, and AEs leading to discontinuation. For a given AE, a subject will be counted once even if he/she has experienced multiple episodes of that particular AE.

In addition, non TEAEs will be summarized or listed separately.

For local tolerability (erythema, scaling, dryness, stinging/burning), data will be summarized for worst score over treatment period, the final score during treatment, as well as scores for each visit.

The quality of life indices, EQ-5D-5L, COMPAQ (including the anchor question), C-DLQI, and DLQI will be summarized descriptively.

Subgroup analyses will be explored by analysis center, age (<18 years, ≥18 years), gender and race if appropriate for efficacy endpoint, and safety endpoints (TEAEs and Local tolerability).

Further details will be provided in the SAP.

9.1.3.1 *Imputation of missing data*

The last observation carried forward (LOCF) will be used to impute efficacy endpoints, where applicable. Non-responder analysis will also be carried out for Binary endpoints.

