9.2 Sample size determination

There is no formal hypothesis to be tested. An estimation approach will be performed. Point estimate and 95% confidence interval will be constructed. Approximately 50 subjects will be enrolled to evaluate the subject reported outcomes (quality of life and satisfaction survey).

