11.5.3. Photographs

CCI

CCI

CCI

12. Health Economics

Not applicable.

CCI

CCI

13. Interim Analyses

CCI

CCI

CCI

14. Changes from Analysis Planned in Protocol

Subgroup analyses were deemed not appropriate and thus were removed.

CCI

CCI

15. Reference List

Not applicable.

CCI

CCI

16. Programming Considerations

All TFLs and statistical analyses will be generated using SAS[®] 9.4 or higher (SAS[®] Institute Inc., Cary, NC, USA). Computer-generated TFL output will adhere to the following specifications.

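### The SAP drops the protocol's rule that adverse events starting before first dose and worsening on treatment count as treatment-emergent, and its readable changes section does not say so

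*SAP*

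**What the plan says.** Protocol 9.1.3 defines a treatment-emergent adverse event (TEAE) by either of two conditions. The first is onset at or after the first dose. The second is "or those AEs with onset prior to first dose of study drug but worsened during treatment". Non-TEAEs are to be summarized or listed apart.

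SAP 11.4 states that the adverse event summaries contain TEAEs only, and these are "treatment-emergent AEs (TEAEs) defined as AEs with an onset date on or after the date of first treatment". Its one readable addition is that an event with no onset date counts as a TEAE. On the denominator it says: "Percentages will be calculated using the total number of subjects in the SAF". SAP Section 11 also sends all safety data to listings.

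SAP Section 14, which records departures from the protocol, reads in its visible part: "Subgroup analyses were deemed not appropriate and thus were removed". It says nothing about the TEAE definition. Parts of 11.4 and of Section 14 are redacted, but the definition sentence in 11.4 is complete.

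**The concern.** The two documents define the same safety quantity differently, and the SAP version is the one that will be programmed. Protocol 9.1 presents the SAP as a more detailed account of the protocol's strategy. It asks the study report to document changes made after the SAP is final. A departure written into the SAP itself escapes that requirement, so Section 14 is where a reader would expect to find it.

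The effect is not confined to the overall TEAE table. Protocol 9.1.3 also plans tables of serious, related, severe, special-interest and discontinuation-related events. Because SAP 11.4 limits event summaries to TEAEs, an event that began before treatment and then became severe, or led to discontinuation, on treatment could leave those tables too. SAP Section 2 foresees use of these analyses in regulatory submissions, publications and promotional material.

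**Working it through.** No figure in the plan needs reproducing. The check compares the two definitions for each kind of event, then sizes one affected subject.

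**Which events are classified differently**

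| Event | Protocol 9.1.3 | SAP 11.4 |
|---|---|---|
| Onset after the first dose | TEAE | TEAE |
| Onset on the day of first treatment, before the evening application, not worsened | Not a TEAE on a strict reading | TEAE |
| Onset date missing | No rule stated | TEAE |
| Onset before the date of first treatment, not worsened | Not a TEAE | Not a TEAE |
| Onset before that date, worsening entered as a new event with on-treatment onset | TEAE | TEAE |
| Onset before that date, worsened on treatment, kept as one record | TEAE | **Not a TEAE** |

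Only the last row loses events. The second and third rows can add events, so the downward direction belongs to the dropped limb alone and not to the SAP definition as a whole. The second row arises because the SAP works by calendar date while, under Protocol 6.1.4, "Applications will be done by the subjects themselves at home in the evening".

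**Can such events exist?** Protocol 7.2.2.2.1 collects adverse events from signature of the consent form, so an event can be on record before treatment. The exposed window runs from consent to the day before first treatment. Protocol Section 4 allows for it ("Prior to subject enrolment, a screening period lasting"), but the maximum length is redacted, so the window cannot be sized. It is empty for a subject who consents and first applies the cream on the same date.

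**Does recording practice close the gap?** Protocol 7.2.2.1.1 treats clinically significant worsening since the first visit as an adverse event. It asks for a new report for each new episode of a chronic disease. No readable text requires a new record when an adverse event already recorded gets worse. The protocol's second limb presupposes that some worsened events keep a pre-dose onset date, since otherwise it would have nothing to act on.

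**Size per affected subject**

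- Denominator: the safety population. The protocol synopsis says: "The Safety population (SAF) consists of the ITT population, who applied at least one dose of treatment".
- Planned enrolment, Protocol 9.2: "Approximately 50 subjects will be enrolled to evaluate the subject reported outcomes".
- Assumption: all of about 50 enrolled subjects apply at least one dose, so N = 50.
- Fall in a row's incidence for each affected subject with no other TEAE in that row = 1/N.
- N = 50: 1/50 = 2.0 percentage points.
- N = 49 (one enrolled subject never treated): 1/49 = 2.04 percentage points.

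These are step sizes, not estimates of the total effect. No event rate is assumed because the documents give none.

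**The case against.** The best case on the other side accepts the mismatch and disputes its consequence.

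- **Worsening is already an adverse event.** Under Protocol 7.2.2.1.1, read with the duty to report every event with an onset date, on-treatment worsening would naturally carry an on-treatment onset, and the SAP would count it. This narrows the gap. It does not close it, because nothing readable requires a separate record for an event already on file.
- **Few or no events.** The pre-treatment window may be short, several criteria refer to a combined screening/baseline visit, and active questioning is described only for visits after enrolment. This stands, and it limits the size.
- **Irritation is captured elsewhere.** Erythema, scaling, dryness and stinging/burning are graded at baseline and at each follow-up visit and tabulated separately, so their worsening stays visible. This is true for those four signs, but tolerability scores do not give the TEAE incidence that the protocol defines.
- **Redaction.** Text after the readable part of 11.4, part of the key definitions in 6.2, and the table and listing indexes are hidden. A worsening rule elsewhere cannot be excluded. It would, however, conflict with the visible restriction of summaries to events meeting the onset rule, so that sentence would still need editing.
- **The data may not support the limb.** The readable event fields are onset date, severity, relationship and outcome, with no date of worsening. This is a fair point about cost, and it is why the fix needs a rule for identifying worsening.
- **No contrast is at stake.** This is correct: the trial is single-arm and descriptive, and its objective is subject-reported outcomes.

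**Conclusion.** The concern holds. The SAP's TEAE definition is narrower than the protocol's in one respect, and the readable changes section does not declare it. The conflict itself is clear from unredacted sentences in both documents.

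The practical effect is probably small and may be nil. It rests on the number of events in the last row of the table above, which the documents do not give, and on a safety population of about 50, which is assumed. The consequence is that TEAE percentages may not be the ones the protocol promised. It should be corrected before database lock because it touches a core safety definition.

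**What to change.** In SAP 11.4, add the protocol's second condition (onset before first treatment but worsened during treatment), with a short rule for how worsening is recognised in the recorded data, such as whether it is a new record or a severity change on the existing one.

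If the narrower definition is intended, declare it in Section 14 and tabulate separately the events that began before treatment and worsened on it. Protocol 9.1.3 would allow events outside the TEAE definition to be listed only, but a table keeps the count that the protocol's definition would have given.

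The cost is one clause in 11.4 or one line in Section 14, one derivation flag, and possibly a check of pre-dose events before database lock. That check will take more work if the case report form holds no dated record of worsening. Reported TEAE incidence may rise slightly.
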